#### **4.4.3 Vital signs**

##### **4.4.3.1 Blood pressure and heart rate**

Pulse rate, supine and orthostatic (2 min) systolic and diastolic blood pressure will be measured at time points specified in the study plan (Table 1) and time schedule during confinement at PET centre/CPU.

Orthostatic vital signs will include supine blood pressure and pulse rate (obtained after at least 10 minutes in a supine position) and standing blood pressure and pulse rate (obtained after 2 minutes in the standing position).

Vital sign assessments and pulse rates will be measured using a semi-automatic blood pressure recording device with an appropriate cuff size.

If possible, for each subject throughout the study, blood pressure will be measured using the same arm and blood pressure cuff.

#### **4.4.4 Bond-Lader Visual Analog Scale (VAS)**

This psychometric test will be collected at the times given in Table 1 to assess self-rated feelings. The first assessment upon admission to the CPU will be a training session to overcome practice effects and ensure optimal performance for the following assessments, which will take place pre-dose on the days of dosing of SQL SR and the day of discharge from the CPU. The second assessment on Day 1 (pre-dose) will be the baseline assessment.

The test being used for this study consists of a total of 16 100-mm lines anchored at either end by antonyms (Bond et al 1974). Participants mark their current subjective state between the antonyms on the line. Each line is scored as millimetres to the mark from the negative antonym.

The scale has a set of opposing adjectives at either end, as listed below:

alert – drowsy, calm–excited, strong–feeble, muzzy–clear headed, well-coordinated–clumsy, lethargic–energetic, contented–discontented, troubled–tranquil, mentally slow–quick witted, tense–relaxed, attentive–dreamy, incompetent–proficient, happy–sad, antagonistic–amicable, interested–bored, withdrawn–gregarious

At the specified time points during the study, subjects are asked to record how they feel at that time by making a vertical mark on the lines. Standardized instructions will be given to each subject before he completes the questionnaire. Study site personnel will check that the scale has been completed by the subject when collecting the questionnaire. The questionnaires will be evaluated using the same ruler for each subject. Date and time of collection and the distance from beginning of the line and the mark made by the subject on the VAS scale will

be recorded in mm in the CRF. If the mark occurs in between two hash marks on the ruler, the more conservative distance, ie, the longer distance will be recorded in the CRF.

#### 4.5 Genetic measurements and co-variables (Not applicable)

#### 4.6 Volume of blood sampling

The total volume of blood that will be drawn from each subject in this study is as follows:

**Table 4 Volume of blood to be drawn from each subject**

Assessment	Sample volume (mL)	n of samples	Total volume (mL)	
Quetiapine plasma concentration	5	12	60	
Safety	Clinical chemistry	11	2x2	44
	Haematology	4	2	8
Serology	10	1	10	
(Additional unforeseeable samples)			(50)	
Total (approximately)			122 (172)	

Depending on whether any extra blood samples will be drawn e.g., for safety reason or to clear the indwelling catheter from saline, it is assumed that the total amount of blood taken will not exceed 172 mL.

#### 4.7 Adverse Events

The methods for collecting adverse events are described below.

##### 4.7.1 Adverse Events

##### 4.7.1.1 Definitions

The definitions of adverse events (AEs), serious adverse events (SAEs) and other significant adverse events (OAEs) are given below. It is of the utmost importance that all staff involved in the study are familiar with the content of this section. The principal investigator is responsible for ensuring this.

##### Adverse event

An adverse event is the development of an undesirable medical condition or the deterioration of a pre-existing medical condition following or during exposure to a pharmaceutical product, whether or not considered causally related to the product. An undesirable medical condition can be symptoms (e.g., nausea, chest pain), signs (e.g., tachycardia, enlarged liver) or the abnormal results of an investigation (e.g., laboratory findings, electrocardiogram). In clinical studies, an AE can include an undesirable medical condition occurring at any time, including run-in or washout periods, even if no study treatment has been administered.

### **Serious adverse event**

A serious adverse event is an AE occurring during any study phase (ie, run-in, treatment, washout, follow-up), and at any dose of the investigational product, comparator or placebo, that fulfils one or more of the following criteria:

- Results in death
- Is immediately life-threatening
- Requires in-patient hospitalisation or prolongation of existing hospitalisation
- Results in persistent or significant disability or incapacity
- Is a congenital abnormality or birth defect
- Is an important medical event that may jeopardise the subject or may require medical intervention to prevent one of the outcomes listed above.

The causality of SAEs (ie, their relationship to study treatment) will be assessed by the investigator(s), who in completing the relevant case report form must answer “yes” or “no” to the question “Do you consider that there is a reasonable possibility that the event may have been caused by any of the following – study medication – other medication?”. For further guidance on the definition of a SAE and a guide to the interpretation of the causality question, see [Appendix B](#) to the Clinical Pharmacology Study Protocol.

Note that SAEs that could be associated with any study procedure should also be reported. For such events the causal relationship is implied as “yes”.

### **Other Significant Adverse Events (OAE)**

OAEs will be identified by the Study Delivery Team Physician in consultation with the appropriate Global Drug Safety Physician during the evaluation of safety data for the Clinical Study Report. Significant adverse events of particular clinical importance, other than SAEs and those AEs leading to discontinuation of the subject from study treatment, will be classified as OAEs. Examples of these are marked haematological and other laboratory abnormalities, and certain events that lead to intervention (other than those already classified as serious), dose reduction or significant additional treatment. For each OAE, a narrative may be written and included in the Clinical Study Report.

#### **4.7.1.2 Recording of adverse events**

AEs will be collected and recorded from Visit 4 (admission to the CPU) and until the follow-up visit (Visit 5). SAEs must be recorded from the time when the informed consent is obtained at Visit 1 until the follow-up visit.

The following variables will be recorded for each AE: AE description, start date and time, stop date and time, maximum intensity, outcome, causality rating (yes or no), and whether it constitutes an SAE or not

The following definitions for intensity rating should be applied:

mild (awareness of sign or symptom, but easily tolerated)

moderate (discomfort sufficient to cause interference with normal activities)

severe (incapacitating, with inability to perform normal activities)

It is important to distinguish between serious and severe AEs. Severity is a measure of intensity whereas seriousness is defined by the criteria in Section 4.7.1.1. An AE of severe intensity need not necessarily be considered serious. For example, nausea that persists for several hours may be considered severe nausea, but not a SAE. On the other hand, a stroke that results in only a limited degree of disability may be considered a mild stroke but would be a SAE.

All AEs spontaneously reported by the subject or reported in response to the open question from the study personnel: “Have you had any health problem during the study day?”/“Have you had any health problems since the previous visit?” or revealed by observation will be collected and recorded in the CRF. When collecting AEs, the recording of diagnoses is preferred (when possible) to recording a list of signs and symptoms. However, if a diagnosis is known and there are other signs or symptoms that are not generally part of the diagnosis, the diagnosis and each sign or symptom should be recorded separately.

Deterioration as compared to baseline in protocol-mandated laboratory values, vital signs, and other safety variables need not be reported as AEs. They will be evaluated in the overall safety analysis. Such deteriorations are only to be reported as AEs if they fulfil any of the SAE criteria or are the reason for discontinuation of treatment with the investigational product. If a deterioration in a laboratory value/vital sign is associated with clinical signs and symptoms, the sign/symptom should be reported as an AE and the associated laboratory result/vital sign should be considered as additional information. Any new or aggravated clinically relevant abnormal medical finding at a physical examination as compared with the baseline assessment should be reported as an AE.

However, all deteriorations should be followed up by the investigator for as long as medically indicated.

Should AEs occur, therapeutic procedures according to standard medical practice will be followed as needed. All AEs should be followed up by the investigator for as long as medically indicated.

Any AEs that are unresolved at the subject’s last AE assessment in the study (ie, at the follow-up visit) are to be followed up by the investigator for as long as medically indicated,

but without further recording in the CRF. AstraZeneca retains the right to request additional information for any patient with ongoing AE(s)/SAE(s) at the end of the study, if judged necessary.

Should an overdose (accidental or deliberate) occur, it must be reported in accordance with the procedures described in Section 8.3, Procedures in case of overdose, regardless of whether the overdose was associated with any symptom or not. All symptoms associated with the overdose should be reported as AEs.

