**Table 1 Study plan**

Visit	1	2	3	4	Residential period			5	
Visit Description	Enrolment	MRI Scana	PET Exam1a	Admission to CPU	SQL SR titration	SQL SR maintenance	PET Exam 2 after SQL SR dose	Discharge Follow-up	
Visit Window (Day)	Within -30 to -4 days	Within -29 to -1 days	Within -7 to -1 days	Day -1	Day 1-4b	Day 5-7b,c	Day 8	Day 9	5-9 days after last dose
Informed consent	X								
Demographic measurements	X								
Medical/surgical history	X								
Physical and neurological examination	X								X
Habits of nicotine, alcohol and caffeine	X								
Vital signs d	X				X e	X e	X	X	X
Electrocardiogram	X			X f		X g		X	
Inclusion/exclusion criteria	X								

Visit	1	2	3	4	Residential period			5
Visit Description	Enrolment	MRI Scan a	PET Exam1a	Admission to CPU	SQL SR titration	SQL SR maintenance	PET Exam 2 after SQL SR dose	Discharge Follow-up
Visit Window (Day)	Within -30 to -4 days	Within -29 to -1 days	Within -7 to -1 days	Day -1	Day 1-4b	Day 5-7 b,c	Day 8	Day 9
								5-9 days after last dose
Clinical chemistry/Haematology	X			X h				X
Urinalysis	X			X h				
Hepatitis B, C, and HIV	X							
Drugs of abuse screen	X							
Production of plaster helmet			X					
MRI		X						
PET after iv administration of (S,S)[18F]FMeNER-D2			X				X i	
Administration of SQL SR once daily in the morning					X	X	X	
Blood sampling for quetiapine PK							X j	

Visit	1	2	3	4	Residential period			5
Visit Description	Enrolment	MRI Scan a	PET Exam 1a	Admission to CPU	SQL SR titration	SQL SR maintenance	PET Exam 2 after SQL SR dose	Discharge Follow-up
Visit Window (Day)	Within -30 to -4 days	Within -29 to -1 days	Within -7 to -1 days	Day -1	Day 1-4b	Day 5-7 b,c	Day 8	Day 9
								5-9 days after last dose
Bond- Lader VAS k				X l	X	X	X	X
Adverse events m				X	X	X	X	X

- a) MRI and PET examination 1 cannot be done on the same day.
- b) In panel B and C the titration period may be removed (i.e. if dose is set to 50 mg) or changed to two days (i.e. if dose is set to 150 mg). The range of total time at CPU may thus be from 6 to 10 days for panel B and C.

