- c) In the unexpected event of technical failure (camera breakdown or the radioligand synthesis fails), the PET examination has to be moved to the nearest working day. Then it is done during the nearest days. In this case the SQL SR maintenance dosing period will be prolonged by 1-3 days (three days if it is moved from Friday to Monday). If this occurs the time the healthy volunteers are confined to the CPU will be prolonged.
- d) Vital signs includes pulse, systolic and diastolic blood pressure supine and again 2 min after standing.
- e) Vital signs will be assessed pre-dose and 6 hours post-dose during SQL treatment days, except for the PET 2 examination day, when vital signs will be assessed only pre-dose.
- f) ECG should be assessed prior to first titration dose, either day -1 or day 1.
- g) ECG should be assessed 6 hours post-dose the third day of steady state (maintenance dose).
- h) Blood sampling for a reduced Clinical chemistry/Haematology and Urinalysis should be repeated on the day of admission to the CPU if these samples were taken (at Enrolment visit) more than 1 week ago.
- i) Radioligand (S,S) [F]F MeNER-D2 to be injected 3.5 h (210 min) post-SRQ SR dose.  
PET measurements to start approximately 5 h post-SQL SR dose.
- j) Venous blood for PK analysis are to be taken 15 min pre-SQL SR dose, and 1, 2, 3, 4, 5, 6, 7, 8, 10, 12 and 24 h post-SQL SR dose.
- k) Bond-Lader VAS should be in the morning pre-dose.
- l) Training –Bond-Lader VAS
- m) Adverse Events (AEs) must be recorded from the admission to the CPU and until the follow up visit. Serious Adverse Events (SAEs) must be recorded from the time when the informed consent is obtained until the follow-up visit.

[figure not shown]

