**Table 3 Identity of investigational product**

Investigational product	Manufacturer	Strengths	Presentation	Formulation number
Quetiapine SR	AstraZeneca	50 mg	Peach oval tablet	F13219
Quetiapine SR	AstraZeneca	200 mg	Yellow capsule shaped tablet	F12840
Quetiapine SR	AstraZeneca	300 mg	Light yellow oval tablet	F12527
(S,S)[  F]FMeNER-D 2	PET centre, [REDACTED]		Solution for intravenous injection	Not applicable

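### Non-serious adverse events are recorded only from Visit 4, after the first radioligand injection at Visit 3, which is the only tracer exposure without quetiapine

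*Protocol*

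**What the plan says.** Section 4.7.1.2 opens the recording of adverse events at admission to the clinical pharmacology unit: "AEs will be collected and recorded from Visit 4 (admission to the CPU) and until the follow-up visit (Visit 5"). Table 1 footnote m agrees: "Adverse Events (AEs) must be recorded from the admission to the CPU and until the follow up visit". The amended Table 1 keeps this footnote unchanged, and neither table marks adverse events under Visits 1 to 3.

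Serious events follow a different rule, given in the next sentence of section 4.7.1.2: "SAEs must be recorded from the time when the informed consent is obtained at Visit 1 until the follow-up visit". Section 4.7.1.1 adds: "Note that SAEs that could be associated with any study procedure should also be reported".

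The Table 1 row "PET after iv administration of (S,S)[18F]FMeNER-D2" is marked at Visit 3 and again on Day 8. The window for Visit 3 is "Within -7 to -1 days", and admission (Visit 4) is on Day -1. The synopsis describes PET examination 1 as a baseline without medication and PET examination 2 as taking place on quetiapine SR. Table 3, on the identity of the investigational product, includes the radioligand with the presentation "Solution for intravenous injection". The synopsis paragraph on duration of treatment counts its two doses together with the quetiapine SR doses.

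**The concern.** A product that the protocol lists as investigational is given intravenously one visit before non-serious adverse event recording begins. Section 2.2 makes the assessment of adverse events a secondary objective. The risk assessment in section 3.2.2 accepts the tracer and the procedures partly because their risks can be monitored within the study. That section itself names venipuncture pain and discomfort from head fixation, which are non-serious events of the kind that could occur at Visit 3.

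The missing injection is also the informative one. At PET examination 2 the tracer is given on top of quetiapine, and the scan is timed around the expected quetiapine peak. Section 3.2.2 lists somnolence, dizziness and orthostatic hypotension as side effects of quetiapine SR. An event on that day cannot readily be assigned to tracer, procedure or quetiapine. PET examination 1 would give a within-subject comparison, but only if events there are recorded to the same standard.

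**Working it through.** The protocol gives no figure to reproduce. The check sets visit windows against recording periods and makes three counts.

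**Inputs**
- Start of non-serious recording: Visit 4, Day -1 (section 4.7.1.2; Table 1 and footnote m, original and amended).
- Start of serious event recording: consent at Visit 1 (section 4.7.1.2).
- First tracer injection: Visit 3, Day -7 to Day -1, no medication (Table 1; synopsis).
- Second tracer injection: Day 8 in Panel A, on quetiapine SR (Table 1).
- Planned subjects: 6 to 9 (synopsis; section 3.1).

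**Gap between first injection and start of recording** = admission day minus PET 1 day.
- Earliest PET 1: (-1) - (-7) = 6 days.
- Latest PET 1: (-1) - (-1) = 0 days, that is, less than a day.
- Section 3.1 has subjects confined to the unit after PET examination 1, so even at 0 days the injection comes before Visit 4.

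**Injections** = 2 x subjects.
- 2 x 6 = 12 and 2 x 9 = 18 planned in total.
- One per subject is at Visit 3, so 6 to 9 of 12 to 18 (half) precede Visit 4. These are all of the quetiapine-free injections.

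**What is and is not captured for the Visit 3 injection**

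| Type of event | Captured? | Basis |
|---|---|---|
| Serious, including procedure-related | Yes | Sections 4.7.1.1 and 4.7.1.2 |
| Non-serious, still present at admission | Yes | Falls inside the recording period |
| Non-serious, resolved before admission | Not clearly | May be elicited at Visit 4, but the stated start does not clearly admit it |
| Non-serious, subject leaves before Visit 4 | Not clearly | Section 3.3.5.2 has the subject asked, but no recording period is open |

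Other assessments do not fill the gap. In Table 1 the only Visit 3 entries are the helmet and the PET examination, with no vital signs, ECG or laboratory tests. On the day of PET examination 2, footnote e limits vital signs to the pre-dose time.

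**The case against.** The strongest case for leaving the text alone has five parts.

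1. Serious events, including procedure-related ones, are recorded from consent. This stands. A reader might infer that the quetiapine-free injection has no adverse event data at all, but the documents do not support that. Only non-serious events are at issue.
2. Subjects who discontinue are to be asked about adverse events (section 3.3.5.2), and the open question in section 4.7.1.2 can cover the time since the previous visit, which at Visit 4 reaches back to Visit 3. This stands in part. Some events will come to light, so neither a dropout nor an early event is necessarily lost. But whether such an event may be entered is left unclear by a rule that starts recording at Visit 4.
3. A reader might see a contradiction with the definition in section 4.7.1.1, under which an adverse event may be one "occurring at any time, including run-in or washout periods, even if no study treatment has been administered". The definition says what can count as an adverse event. It does not set a collection period, and the protocol is consistent on when recording starts. The two fit poorly together, but they do not contradict each other.
4. No objective names tracer safety, the injected mass is about 5 micrograms, and sections 3.4.1.4 and 3.4.5 mention the ligand separately from the investigational product. With so few subjects little could be learned: zero events would leave a one-sided 95% upper limit of 1 - 0.05^(1/6) = 39% for 6 subjects, or 1 - 0.05^(1/9) = 28% for 9. This limits the importance of the point. It does not justify omitting the record, because the secondary objective covers adverse events generally and Table 3 does list the tracer.
5. Summarising events separately for the tracer-only period and the quetiapine period is analysis detail that sections 6.3.3 and 6.5 leave to the SAP. This stands, and it is not part of the point.

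**Conclusion.** The point holds for non-serious adverse events only. Followed as written, the protocol leaves non-serious events at or after the first tracer injection outside the recording period, or dependent on being elicited later. This affects 6 to 9 of 12 to 18 planned injections and 0 to 6 days per subject. The share of one half counts injections. It is not an estimate of lost events, for which the protocol gives no basis. The Visit 3 window might suggest a gap of seven days, but admission on Day -1 limits it to six.

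The counts assume that every subject has both injections and that no subjects are added as replacements. The consequence is confined to the description of safety: tracer and procedure events cannot be separated from quetiapine events by comparing the two PET days within a subject. Occupancy and its relation to dose and plasma concentration are untouched. This is a cheap improvement to a stated rule, not a flaw that threatens the study.

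**What to change.** Change section 4.7.1.2, the adverse event row of Table 1 (add a mark at Visit 3) and footnote m so that recording of all adverse events starts no later than the first radioligand injection at Visit 3. Starting at consent, as already done for serious events, would serve equally well and would give both kinds of event the same start. Either version also settles whether events reported at Visit 4 or at an early discontinuation can be entered.

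The cost is amendment wording, one extra adverse event page at an existing visit, and slightly more adverse event data to clean and list. No new visit or procedure is needed.

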#### **4.7.1.3 Reporting of serious adverse events**

Investigators and other site personnel must inform appropriate AstraZeneca representatives of any SAE that occurs in the course of the study within 1 day (ie, immediately but no later than the end of the next business day) of when he or she becomes aware of it.

All Serious Adverse Events (SAE) must be reported to Clinical Drug Safety, AstraZeneca Marketing Company Sweden, within one day (that is immediately but not later than the end of the next business day) by fax [REDACTED]. Clinical Drug Safety will forward the SAE report to the applicable AstraZeneca R&D. The monitor should also be informed when an SAE has occurred.

For any product provided by AstraZeneca, the Investigator's responsibility of safety reporting to the Medical Products Agency and Ethics Committee is delegated to AstraZeneca.

For any concomitant product, i.e., products not provided by AstraZeneca, it is the responsibility of the investigator to report to the Medical Products Agency any SAE with a causality related to the concomitant medication.

The AstraZeneca representative will work with the investigator to compile all the necessary information and ensure that the appropriate AstraZeneca Drug Safety Department receives a report by day one for all fatal and life-threatening cases and by day five for all other SAEs.

Follow-up information on SAEs must also be reported by the investigator within the same time frames.

If a non-serious AE becomes serious, this and other relevant follow-up information must also be provided to AstraZeneca within 1 day as described above. . For a non-serious AE that become serious but which is not fatal or life-threatening a report should be received within 5 days.

All SAEs have to be reported, whether or not considered causally related to the investigational product or to the study procedure(s). All SAEs will be recorded in the Case Report Form. The investigator and/or Sponsor are responsible for informing the Ethics Committee and/or the Regulatory Authority of the SAE as per local requirements.

AstraZeneca is responsible for informing the Ethics Committee and the Regulatory Authority of the SAE as per local requirements.

